# E.1f Interventions

- SBIRT. All participants randomized to SBIRT will receive an on-the-spot alcohol brief intervention (CETA-BI) and be categorized as low or moderate/high severity. Moderate/high severity is defined as one or more of: (a) AUDIT scores indicating moderate-to-severe AUD (≥12 for women; ≥16 among men); (b) meeting validated symptom criteria for depression (≥16 on CES-D),  (c) trauma/anxiety (≥2.5 on HTQ),  (d) substance use (≥27 on ASSIST).  Participants who are low severity will not receive any additional treatment. Participants who are moderate/high severity will be connected to a CETA counselor and will begin full CETA treatment. This will involve approximately 6-12 weekly CETA sessions. CETA sessions will be conducted in a private setting mutually agreed upon by the counselor and participant (this could be in the health clinic or some other community-based setting where the participant feels comfortable). Data collected for these intervention participants will include the Improving Your Health worksheet (during the BI session), the Client Monitoring Form (during CETA sessions) and the Alcohol Timeline Followback (completed at both the BI and subsequent CETA sessions. All of these measures are included in Rascal.
- TAU. In October 2019, Mantapala health workers and supervisors were trained in mhGAP-HIG, which is a mental health service provision guide for use in humanitarian settings; this training was led by staff from United Nations High Commissioner for Refugees. This training did *not* include evidence-based psychological interventions (e.g., CETA). Participants randomized to TAU will be referred to the existing services that exist in the health clinic located in Mantapala refugee settlement. This clinic is staffed by eight clinical staff who provide clinical assessments, primary care, basic counseling, and limited specialized services (e.g., maternal and child care, HIV treatment). More specialized services are referred to the District Hospital in Nchelenge, which is the nearest town approximately 50 kilometers away.

# E. Ig Follow-up Assessments

Participants will be asked to complete two follow-up study assessments at 6- and 12-months post-baseline. We will ask the participants to complete the same ACASI questionnaire as baseline. We expect these study visits to take approximately one hour. Participants will be eligible to complete these assessments within a +/- one month window around the 6 and 12 month scheduled assessments. If they do not complete the assessment within that window it will be considered a missed visit. Once participants complete the 12-month visit, they will exit the study.

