### E.1e Randomization and Enrollment into the Trial

Participants who complete the full baseline assessment and are fully eligible for the trial (have met all inclusion and no exclusion criteria) will be randomized and enrolled into the RCT. Randomization will be on a 1:1 basis, stratified by gender and site (Mantapala settlement or host community) and symptom severity (low or moderate/high). Participants will be randomized to SBIRT or treatment as usual (TAU) control. The RA will allocate participants to study conditions using a series of sealed, opaque envelopes. RAs and data analysts will be blinded. Participants will be notified immediately about the result of the randomization.

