### F. STATISTICAL PROCEDURES

Provide sufficient details so that the adequacy of the statistical procedures can be evaluated including power calculations to justify the number of participants to be enrolled into the study. Definitions of subject terms such as enrolled and accrued as used for Rascal submissions can be found in the Subjects section

The primary outcome is the difference in change in AUDIT score from baseline to 12-month follow-up between SBIRT and TAU. Using baseline data from an ongoing study of CETA-BI + Full CETA in Lusaka, we estimated the sample size required to estimate a moderate treatment effect (Cohen's d=0.5) with 90% power would be 172 (86 per arm). Given the stratified sampling, clustering, planned subgroup analyses, and possible attrition, our study will require a total sample size of 400.

The primary analysis will use mixed effects regression to estimate the difference in change in AUDIT scores between the treatment groups. Secondary analyses will include: a) treatment effectiveness for secondary outcomes; b) moderator/subgroup; c) mediators; d) predictors of treatment completion; e) longitudinal analysis of weekly symptom change (on the CMF and Alcohol TLFB for CETA participants; and g) mixed methods analysis based on best practice guidelines for exploring implementation data.

Qualitative data from the implementation interviews will be transcribed and any identifiable information will be redacted. Once transcribed, the audio recordings will be destroyed. These data will then be analyzed by members of the research team using thematic analysis whereby research staff read the full set of transcripts and develop codes using a subset of those transcripts. Once a codebook has been developed, it will be applied to the full set of transcripts with codes added as needed. We anticipate the main domains will include adoption, acceptability, appropriateness, feasibility, and reach/access of SBIRT.

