- 3) Each participant will be assigned a unique study ID number, and all data (e.g., ACASI data, CMF/TLFB data, implementation data) will be coded with ID numbers only and will not contain identifying information. These data will be stored on the encrypted system with restricted access to essential investigators and staff. We will not obtain signatures on the consent form/information sheet. We will only collect sensitive data/identifying information (names, phone numbers, and addresses) from participants for purposes of contacting participants to schedule study visits. An encrypted spreadsheet linking participant names, phone numbers, and addresses with ID numbers will be stored separately from the coded data. This personally identifiable information will be stored on an encrypted endpoint computer in a locked office within the study office in Kawambwa. Only essential staff for conducting participant follow-ups will have access to this file. Columbia personnel will not have access to sensitive data/identifying information. Following the end of the study, the link and all personally identifiable information will be destroyed such that all data are completely de-identified.
- 4) Paper-based data (Client Monitoring Form, Alcohol TLFB, and Improving Your Health worksheets, and notes taken during qualitative interviews and discussions) will be coded and securely stored in locked file cabinets in the study team's locked offices. They will be entered into an encrypted database stored on an encrypted shared data system.
- 5) Qualitative interviews in Aim 2 will be recorded with permission from the participants (no other activities will have audio recording). Recordings will be destroyed after interviews are transcribed. We expect transcription of audio files to be done within one to two weeks after the interview session. The oral study introduction will not be included in the recording and we will train research assistants to avoid mentioning personal identifying information during the course of the interview. Any personal information that is discussed during the interview will be redacted from study transcripts.

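### Does counting a 12-month AUDIT taken after month 13 as a missed visit weaken the primary outcome?

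*Combined protocol and SAP*

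**What the plan says.** Section E.1g (Follow-up Assessments) sets a single rule for both follow-ups: "Participants will be eligible to complete these assessments within a +/- one month window around the 6 and 12 month scheduled assessments". It continues: "If they do not complete the assessment within that window it will be considered a missed visit". After the last assessment, "Once participants complete the 12-month visit, they will exit the study". For the primary outcome the window therefore runs from month 11 to month 13, and no exception is made for that visit.

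Section F places the primary outcome there: "The primary outcome is the difference in change in AUDIT score from baseline to 12-month follow-up between SBIRT and TAU". The analysis is a mixed effects regression. Section F does not mention missing or out-of-window values. On numbers it calculates 172 participants (86 per arm) for d = 0.5 with 90% power, then states: "Given the stratified sampling, clustering, planned subgroup analyses, and possible attrition, our study will require a total sample size of 400".

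Section G says what contact data are held and why: "We will only collect sensitive data/identifying information (names, phone numbers, and addresses) from participants for purposes of contacting participants to schedule study visits". It adds that "Following the end of the study, the link and all personally identifiable information will be destroyed".

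**The concern.** The two visits do not matter equally. A missed 6-month AUDIT still leaves the baseline and 12-month values that define the primary contrast. A missed 12-month AUDIT removes the endpoint itself, and nothing later can replace it. The same window nevertheless applies to both.

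The rule also reads as a limit on collection, because it says when a participant is eligible to complete the assessment. A research assistant following it would probably not offer the questionnaire in month 14, even though the trial holds the contact details needed to find that person. The primary model would then have to assume that values are missing at random where some could have been observed. If people who are hard to reach drink more, and there are more of them in one arm, the estimate could be biased. At the least, precision would be lost.

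**Working it through.** **1. The plan's own figure.** A two-sample t-test with d = 0.5, 90% power and two-sided alpha 0.05 (alpha is not stated, so it is assumed) needs 85.03 per arm. Rounded up, that is 86 per arm, or 172 in total, which matches Section F. The planned 200 per arm could fall to 86, a loss of 1 − 86/200 = 57%, before power at d = 0.5 dropped to about 90%, if there were no design effect.

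**2. Precision.** Assumptions, none of them in the documents: 200 per arm, three visits, equal correlation of 0.5 between visits, separate means by arm and visit, only month 12 missing, and a late share m of 5%, 10% or 15% (20, 40 or 60 of 400).

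- With complete data, SE of the difference in change = √(2 × 2(1 − 0.5)/200) = 0.100 SD.
- Given the first two visits, the residual variance of the 12-month value is 1 − 2(0.5²)/(1 + 0.5) = 2/3. Only that part of the variance grows with missingness, so the SE is multiplied by √(1/3 + (2/3)/(1 − m)).

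| Late share m | SE rise, none reached | SE rise, half reached | Difference (points) |
|---|---|---|---|
| 5% | 1.74% | 0.85% | 0.89 |
| 10% | 3.64% | 1.74% | 1.90 |
| 15% | 5.72% | 2.67% | 3.05 |

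**3. Power at d = 0.5.** Power = Φ(0.5/(SE × √D) − 1.96), where D is an assumed design effect. With correlation 0.5 the change score has SD 1, so d is on the same scale as the SE.

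| Missing at month 12 | D = 1 | D = 1.5 | D = 2 |
|---|---|---|---|
| 0% | 99.9% | 98.3% | 94.2% |
| 5% | 99.8% | 98.0% | 93.5% |
| 10% | 99.8% | 97.6% | 92.7% |
| 15% | 99.7% | 97.1% | 91.7% |

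Halving the missing share from 10% to 5% gains 93.5 − 92.7 = 0.8 points at D = 2, and less at smaller D. Halving it from 15% to 7.5% (93.1%) gains 1.4 points at D = 2.

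**4. Bias from leaving late values out.** Bias = (difference in late share between arms) × (late-minus-on-time difference in outcome). It is zero if late shares, and that difference, are the same in both arms. If late shares differ by 5 points and late responders differ by 0.25 to 0.5 SD:

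- 0.05 × 0.25 = 0.0125 SD and 0.05 × 0.5 = 0.025 SD.
- Divided by the SE of 0.1036 at 10% missing, that is 0.12 to 0.24 of an SE. Coverage of a 95% interval would be 94.8% to 94.3%.

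These are upper figures, because a mixed model removes whatever part of the difference the baseline and 6-month values predict.

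**5. Dilution from putting late values in.** Suppose late values are taken at month 15 but analysed as month 12, and a 0.5 SD effect fades to zero over the following 12 months. Dilution if all are reached = m × 3 × (0.5/12) = 0.006, 0.013 or 0.019 SD for m = 5%, 10% or 15%. That is the same order as the bias in step 4.

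**The case for a change.** The strongest argument is that the choice is lopsided. A late, dated AUDIT can be modelled at its actual time or left out of an in-window analysis, whereas one never collected cannot be recovered once the contact link is destroyed. Modelling actual time would also avoid the dilution in step 5. This is a fair case for a wider final window, and some trials would choose one.

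It does not make the plan's choice wrong. The documents do not say how many participants would be late, or whether those not reached in a window two months wide could be reached by a longer search. The alternative has costs of its own: more field work, longer retention of names and addresses in a setting where the protocol stresses breach of confidentiality, and more spread in time since baseline. At an assumed 1 to 3 hours of tracing per person plus a one-hour visit, the extra field work comes to about 30 hours (20 × 1 + 10 visits) to 240 hours (60 × 3 + 60 visits).

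A second argument is that the 400 must also cover clustering and subgroup analyses, neither of which is given a size, and that the true effect may be smaller. At an assumed d = 0.3 and D = 1, the formula in step 3 gives 85.1% with complete data, 82.5% with 10% missing and 83.9% with 5% missing. Halving the missing share then gains 1.4 points, which is still modest, and d = 0.3 is not the plan's effect size.

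One part stands. Section F should ideally say how missing or out-of-window 12-month values enter the model. E.1g classifies a visit; it does not order that a late AUDIT, if one were taken, be discarded. This is a detail the analysis section leaves open, and it does not make the window faulty.

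**Conclusion.** The concern does not hold. The reading of the text is correct: month 13 is the upper limit, and the visit that carries the primary outcome has no exception. But a symmetric window stated in advance and applied alike to both arms is a normal design decision, consistent with an outcome defined at 12 months, and it leaves every figure in the plan intact. The total of 400 against a calculated 172 already names attrition among its reasons.

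On assumed late shares of 5% to 15%, the SE rises by 1.7% to 5.7%, and power at d = 0.5 stays at or above 91.7% even with a design effect of 2. Reaching half of the late participants would return 0.8 points of power at a 10% late share and 1.4 at 15%, both at that design effect. Bias is possible but not shown; under the assumptions above it is at most about a quarter of an SE and no clearer than the dilution it would be exchanged for. The late shares, correlation, design effects, arm difference and fade rate are all illustrative. A high late share that differed strongly between arms would change the picture, but nothing in the documents points to one.

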## E.2 Procedures for Implementation Interviews

### E.2a Recruitment

We will conduct implementation interviews with a subset of participants enrolled in the RCT as well as other relevant stakeholders. Participants in the implementation interviews include participants enrolled in the RCT who received SBIRT (n=30), SBIRT counselors (n=15), or is a humanitarian policymakers or program officials whose position has relevance for the implementation of SBIRT in humanitarian settings (n=15). We will purposively recruit a subset of 30 RCT participants who received SBIRT selected using maximum variation sampling to ensure they represent both refugee and host community members, participants with a range of alcohol and substance use patterns at baseline, and variations in attendance and intervention response. Participants will be invited to complete the implementation interview by the RA at their 6-month follow-up interview. Fifteen SBIRT counselors will be invited by an RA to participate in an implementation interview at the end of their final SBIRT session. We will purposively select counselors to reflect variation in the following characteristics: number of SBIRT and CETA sessions delivered, community membership (refugee vs. host), and competency as identified by the clinical supervisor. Fifteen humanitarian stakeholders (e.g., policymakers and program officials) will be invited to participate in the study interview by a member of our research team throughout the study period. We will select these stakeholders based on their knowledge of the project and the relevance of their role in its implementation.

Recruitment activities will be conducted by the Zambia-based team at WiLDAF and CARE Zambia. Columbia investigators will not be involved in the recruitment process and will not interact directly with potential study participants.

## E.2b Informed Consent

Trial participants who are selected to complete an implementation interview will be reminded by the RA of the original study consent form (see section E.1b), which includes information about potential participation in the implementation interview. The RA will offer to provide a copy of the consent form for their review, if interested. They will review the study information sheet again with the participant prior to initiating the implementation interview and provide an opportunity for the participant to ask any questions before beginning.

Selected providers and invited humanitarian stakeholders who have not been previously enrolled in the study will meet with a trained WiLDAF RA in a secure, private study location in Mantapala settlement, another secure office, or by phone to review details about the study. All participants will provide verbal informed consent as with our previous studies in Zambia (including AAAT1592, which was also conducted in Mantapala) given the sensitivity of signing documents and the increased risk this has for a breach of confidentiality. Similar to participants enrolled in the trial, the Informed Consent Process will begin with a concise and focused presentation of the key information about the research study. The RA will review the study information sheet with the potential participant, which includes information on study purpose, study procedures, risks/benefits, and voluntary participation. All RAs will be trained in human subjects research ethics using the Johns Hopkins Institutional Review Board field guide, which has been previously used to train research staff working in humanitarian settings.

Consents will be available in English and Bemba. In our previous study in Mantapala, we found that some participants prefer speaking Swahili at times: we will also have an onsite translator/interpreter for participants who may also want to speak Swahili. This Informed Consent Process presents information in

sufficient detail relating to the research study. All potential participants, including the participants already enrolled in the RCT, will have the opportunity to discuss the information.

### E.3c Interviews

Mixed methods interview guides will be based on the Johns Hopkins Dissemination and Implementation measure, which explores adoption, acceptability, appropriateness, feasibility, scalability, sustainability and reach/access of SBIRT. Interview guides will be adapted to the stakeholder group (SBIRT participant, counselor, other stakeholder), but will cover similar domains. The interview guides include questions assessing these constructs quantitatively using a Likert scale as well as open-ended questions and probes that are adapted over the course of the study. These guides are included in Rascal. While adaptations to the specific questions may evolve over the course of the interviews, if any modifications are made to the questions or probes that extend beyond the constructs described above, we will submit a modification to the IRB. These interviews will be administered by a WiLDAF RA in a private location, or a location requested by the study participant. Implementation interviews will be audio recorded. We expect the interview will take approximately one hour to complete. Interviews with humanitarian stakeholders may take place by phone/Zoom.

## E.2 Procedures for Exit Interviews

### E.2a Recruitment

We will conduct exit interviews with a subset of 30 participants enrolled in the RCT within one month after they have finished their 12-month follow-up assessment. We will purposively recruit a subset of 30 RCT participants using maximum variation sampling to ensure they represent both refugee and host community members, participants allocated to SBIRT and TAU, and participants with a range of alcohol and substance use patterns. Participants will be invited to complete the implementation interview by the RA at their 12-month follow-up interview.

Recruitment activities will be conducted by the Zambia-based team at WiLDAF and CARE Zambia. Columbia investigators will not be involved in the recruitment process and will not interact directly with potential study participants.

## E.2b Informed Consent

Trial participants who are selected to complete an exit interview will review the study information sheet covering the objectives, procedures, risks, and benefits for the exit interview with an RA. The RA will offer to provide a copy of the information sheet for their review, if interested. They will review the study information sheet again with the participant prior to initiating the implementation interview and provide an opportunity for the participant to ask any questions before beginning.

Information sheets will be available in English and Bemba. In our previous study in Mantapala, we found that some participants prefer speaking Swahili at times: we will also have an onsite translator/interpreter for participants who may also want to speak Swahili. This Informed Consent Process presents information in sufficient detail relating to the research study. All potential participants, including the participants already enrolled in the RCT, will have the opportunity to discuss the information.

### E.3c Interviews

The interviews will explore perceptions of the accuracy of self-reported alcohol and other drug use behaviors among study participants as well as the factors that may influence the accuracy of reporting. We will not ask participants to report on any specific study participants or their own reporting, but rather their perceptions about reporting generally. These guides are included in Rascal. While adaptations to the specific questions may evolve over the course of the interviews, if any modifications are made to the questions or probes that extend beyond the constructs described above, we will submit a modification to the IRB. These interviews will be administered by a WiLDAF RA in a private location, or a location requested by the study participant. Exit interviews will be audio recorded. We expect the interview will take approximately 15-30 minutes to complete.

### F. STATISTICAL PROCEDURES

Provide sufficient details so that the adequacy of the statistical procedures can be evaluated including power calculations to justify the number of participants to be enrolled into the study. Definitions of subject terms such as enrolled and accrued as used for Rascal submissions can be found in the Subjects section

The primary outcome is the difference in change in AUDIT score from baseline to 12-month follow-up between SBIRT and TAU. Using baseline data from an ongoing study of CETA-BI + Full CETA in Lusaka, we estimated the sample size required to estimate a moderate treatment effect (Cohen's d=0.5) with 90% power would be 172 (86 per arm). Given the stratified sampling, clustering, planned subgroup analyses, and possible attrition, our study will require a total sample size of 400.

The primary analysis will use mixed effects regression to estimate the difference in change in AUDIT scores between the treatment groups. Secondary analyses will include: a) treatment effectiveness for secondary outcomes; b) moderator/subgroup; c) mediators; d) predictors of treatment completion; e) longitudinal analysis of weekly symptom change (on the CMF and Alcohol TLFB for CETA participants; and g) mixed methods analysis based on best practice guidelines for exploring implementation data.

Qualitative data from the implementation interviews will be transcribed and any identifiable information will be redacted. Once transcribed, the audio recordings will be destroyed. These data will then be analyzed by members of the research team using thematic analysis whereby research staff read the full set of transcripts and develop codes using a subset of those transcripts. Once a codebook has been developed, it will be applied to the full set of transcripts with codes added as needed. We anticipate the main domains will include adoption, acceptability, appropriateness, feasibility, and reach/access of SBIRT.

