## E.1c Screening

Participants who provide informed consent will complete a brief demographics questionnaire and the Alcohol Use Disorders Identification Test (AUDIT),  $^{20}$  which is a 10-item validated screening tool for unhealthy alcohol use. These measures will be administered through audio computer assisted self-interviewing (ACASI) and available in English and Bemba. The participant will self-complete the measures with the RA nearby in case the participant has any questions. ACASI will automatically calculate the total AUDIT score, which will inform the RA if the participant is eligible for the trial based on the alcohol criterion ( $\geq 8$  for men and  $\geq 4$  for women). Participants who are ineligible for the trial will be thanked for their time and provided with a list of relevant programs and services for mental health in Mantapala settlement and the surrounding area. Participants who are eligible will continue with the baseline assessment.

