### E.1d Baseline Assessment

The full baseline assessment will include previously translated and piloted in Bemba measures of our secondary mental health and substance use outcomes. These measures include: depression (Center for Epidemiologic Studies-Depression scale; CES-D); generalized anxiety (Generalized Anxiety Disorder-7 scale; GAD-7); trauma symptoms (Harvard Trauma Questionnaire; HTQ; substance use (Alcohol, Smoking, and Substance Involvement Screening Test; ASSIST); and sleep (Sleep Scale for the Medical Outcomes Research Study). We expect the baseline assessment to take approximately one hour to complete (including the Demographics and AUDIT, which are part of the screening).

Research Assistants will be trained to identify signs of acute alcohol withdrawal and severe mental illness. Participants will also be screened for suicidal ideation during the ACASI assessment. If the RA believes that the participants may be ineligible for randomization and enrollment into the trial on any of these criteria, they will contact an on-site study clinical supervisor for assessment. The clinical supervisor will determine if the participant is ineligible based on these criteria and, if so, will assist the participant in accessing immediate services.

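### The primary mixed model does not say how baseline AUDIT or the randomisation strata enter; naming one common-baseline, strata-adjusted model gives a modest gain in precision from data already collected.

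*Combined protocol and SAP*

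**What the plan says.** Section F carries the whole quantitative analysis plan. It defines the endpoint: "The primary outcome is the difference in change in AUDIT score from baseline to 12-month follow-up between SBIRT and TAU". It then gives the method: "The primary analysis will use mixed effects regression to estimate the difference in change in AUDIT scores between the treatment groups". It does not state the covariates, the handling of baseline AUDIT, the role of the 6-month visit, the coding of time or the covariance structure.

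Section E.1e says that randomisation is 1:1 and "stratified by gender and site (Mantapala settlement or host community) and symptom severity (low or moderate/high"). Section F does not list these factors as model terms. Stratification appears there only as a reason for the sample size: "Given the stratified sampling, clustering, planned subgroup analyses, and possible attrition, our study will require a total sample size of 400". The same sentence names clustering, with no unit and no term in the model. Section F also plans further analyses: "Secondary analyses will include: a) treatment effectiveness for secondary outcomes; b) moderator/subgroup; c) mediators".

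Baseline AUDIT doubles as the eligibility screen. In section E.1c, "ACASI will automatically calculate the total AUDIT score, which will inform the RA if the participant is eligible", and section E.1d counts that score within the baseline assessment ("including the Demographics and AUDIT, which are part of the screening"). Section D.1 sets the entry cut-offs at 8 for men and 4 for women. Section E.1f counts an AUDIT of at least 16 for men or 12 for women as one route to moderate/high severity.

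**The concern.** At least two standard models fit the wording of section F. One is the ordinary arm-by-time mixed model with a free baseline mean in each arm. The other constrains the arms to share one baseline mean, which randomisation justifies because AUDIT is measured before allocation. Both estimate the same difference in change, but they give different estimates and standard errors in a given data set. With complete data the first reduces to a comparison of change scores, and in large samples that is never more precise than a baseline-adjusted contrast.

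The width of the interval for the primary effect is at stake and, to a smaller degree, precision in the planned subgroup analyses. So is a choice of primary model that would otherwise be made after the data are seen. Leaving out stratification factors that predict outcome also tends to make the reported SE too large.

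**Working it through.** **The plan's own figure.** Section F gives 172 participants (86 per arm) for d=0.5 with 90% power and states no alpha. With two-sided 0.05 assumed, the two-sample t solution is 85.03 per arm, which rounds up to 86; power at 86 per arm is 90.3%. The figure reproduces. On the same basis power is 99.9% at 200 per arm and 99.4% at 160 per arm (an assumed 20% loss).

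**Closed form.** Let rho be the correlation of baseline with 12-month AUDIT and k the baseline SD divided by the 12-month SD. The documents give neither. In units of the 12-month variance, a change score has variance k² + 1 − 2·rho·k and a baseline-adjusted contrast has 1 − rho². The ratio, adjusted to change, is (1 − rho²)/(k² + 1 − 2·rho·k).

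- k=0.7: 0.85, 0.95 and 1.00 at rho 0.3, 0.5 and 0.7. For example, 0.91/(0.49 + 1 − 0.42) = 0.91/1.07 = 0.85.
- k=0.8: 0.78, 0.89 and 0.98.
- k=1: 0.65, 0.75 and 0.85.
- rho=k: exactly 1.00, so no gain.

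Two design features pull the gain down. The entry cut-offs can narrow the baseline SD and so lower k. Stratifying on severity, taken as defined in section E.1f, already balances part of baseline AUDIT between the arms.

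**Trial-level simulation with the protocol's cut-offs.** Assumptions: AUDIT mean 8 and SD 7 before selection, rounded to 0–40; 60% men; 30% host community; blocks of 4 within 8 strata; 400 randomised; 10% missing at 6 months and 20% at 12 months, at random; no clustering; 3,000 trials per scenario. Reliability of 0.4, 0.6 and 0.8 gives rho 0.29, 0.46 and 0.68 with k 0.77, 0.79 and 0.86. Severity is met through AUDIT alone, or a random 60% also qualify on other criteria. Plain means arm-by-time without strata; named means common baseline with strata.

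| rho | Others qualifying | SD, plain | SD, named | Variance ratio | Mean SE, plain | Mean SE, named |
|---|---|---|---|---|---|---|
| 0.29 | 0% | 0.684 | 0.660 | 0.93 | 0.733 | 0.668 |
| 0.29 | 60% | 0.711 | 0.659 | 0.86 | 0.733 | 0.668 |
| 0.46 | 0% | 0.609 | 0.598 | 0.96 | 0.629 | 0.595 |
| 0.46 | 60% | 0.623 | 0.597 | 0.92 | 0.628 | 0.594 |
| 0.68 | 0% | 0.469 | 0.467 | 0.99 | 0.466 | 0.455 |
| 0.68 | 60% | 0.470 | 0.462 | 0.97 | 0.467 | 0.455 |

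The true variance is therefore 1% to 14% lower. At the top of the range the plain model would need 400/0.86 = 465 participants to match, or 65 more. The 95% half-width there, from the true SDs, falls from 1.96 × 0.711 = 1.39 to 1.96 × 0.659 = 1.29 AUDIT points. At the bottom it is 0.92 for both.

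**Source of the gain.** A common-baseline model without strata had an SD of 0.659, against 0.660 with them. Almost all the precision comes from baseline AUDIT.

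**Reported SE.** At rho 0.29 with AUDIT-only severity, the plain model's SE is 0.733/0.684 = 1.07 times its true SD, and its coverage is 96.4% against 95.2% for the named model. Part of the narrowing in reported intervals is removal of this excess. At rho 0.68 with AUDIT-only severity, the reported SE falls about 2% but the true SDs hardly differ. The named model's SE there is 0.455/0.467 = 0.974 of its SD, about two Monte Carlo standard errors (1/√6000 = 1.3%) below 1. That 2% should not be counted as gain.

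**Power.** With an effect of 0.5 baseline SDs under the same assumptions, plain against named gives 91–92% against 95%, 97% against 98%, and above 99% for both, at rho 0.29, 0.46 and 0.68.

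**The case against.** The strongest reply is that section F does not exclude the recommended model. If the team already intends to adjust for baseline, the only benefit is prespecification. That stands, and it limits the priority.

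Every magnitude rests on inputs that the documents do not give, and the closed form includes a gain of zero. The 14% needs a low correlation and a random 60% meeting other severity criteria independently of AUDIT; with AUDIT-only severity the reductions are 7%, 4% and 1%. This also stands.

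A named model with only within-person covariance would ignore the clustering that section F cites, and the gain has not been tested under clustering. This is right, and the fix allows for it.

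A reader might infer more than the documents support:

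- **That the planned analysis is biased or underpowered.** Neither follows: the free-baseline model is unbiased under randomisation, and 400 is well above the reproduced 172.
- **That the plan commits to a change-score analysis.** Its wording leaves this open.
- **That the gain is 15% to 35% of the variance.** That needs equal SDs at baseline and 12 months, and it ignores the entry cut-offs and the severity stratum.
- **That the strata add precision.** The simulation shows no gain from them beyond baseline AUDIT, though it gave them little prognostic value of their own.
- **That a common-baseline model rescues participants with missed visits.** An ordinary arm-by-time mixed model also keeps them through their baseline record.

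**Conclusion.** The point holds as a modest improvement. Section F leaves open how baseline AUDIT and the strata enter the primary model, and one reading that fits its text gives up precision that the collected data can supply. Against that reading, the named model lowers the true variance by about 1% to 14%, at most about 65 participants' worth of 400. This assumes correlations of 0.29 to 0.68, SD ratios of 0.77 to 0.86, 20% missing at 12 months and no clustering. There is no gain from baseline adjustment if the correlation equals the SD ratio.

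Baseline AUDIT supplies nearly all of the gain. The case for the strata is that the analysis then matches the randomisation, and that the SE is not overstated if they predict outcome. Priority is low to moderate.

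**What to change.** Name one primary model in section F:

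- a longitudinal mixed model with baseline, 6-month and 12-month AUDIT as outcomes;
- categorical time and unstructured within-person covariance;
- a common baseline mean across arms;
- gender, site and severity, each with its interaction with time;
- the cluster term that the sponsor has in mind, with its unit stated, since clustering is a stated reason for the sample size;
- the 12-month arm contrast as the primary estimate.

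Because the baseline mean is common, this contrast is the difference in change from baseline, so the stated primary outcome need not change.

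The cost is SAP wording and a few degrees of freedom: nine strata-by-time parameters (three factors at three visits) and one arm parameter fewer, plus the cluster term. No new data are needed. Section E.1e randomises only "Participants who complete the full baseline assessment and are fully eligible for the trial", so baseline AUDIT and the strata should be on record for everyone allocated.
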